Prior to the start of the study, a randomization schedule will be constructed with block randomization using web-based software. Patients will then be allocated to one of two groups: Topical tranexamic acid or Placebo (saline). Group assignments will be concealed in opaque sealed envelopes with a numerical code of consecutive numbers reflecting patient enrollment. Envelopes will be stored with the pharmacy staff in charge of drug preparation. The pharmacy staff, which will have no patient contact, will remain un-blinded. The pharmacy staff will maintain the master key identifying which patients received the study drug and which patients received the placebo. Physicians, residents, hospital staff, and patients will be blinded to group assignment.

Eligible patients will be offered study enrollment following the screening protocol documented above in the “Screening procedures and who will perform them” section. The PI, Co-Investigator, [name], or the orthopedic surgery resident that is on call during the time of the patients’ hospital admission will obtain informed consent using the informed consent form approved by the IRB. Before a resident can serve as a consenter, he or she must first complete the training protocol found on the form “Educational Plan For Consenters.”

Topical (*Intra-Articular*) Tranexamic Acid and Transfusion Rates Following Hip Hemiarthroplasty

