Following surgery, the patient will be admitted to the hospital per the standard of care. The length of inpatient stay following this procedure is approximately 3 to 4 days, however this may vary. Following discharge from the hospital, patients will follow up with the treating surgeon at two outpatient visits (one at approximately 2 weeks, a second at 4-6 weeks). These visits are the regularly scheduled post-operative visits as part of routine care. The methods and types of data to be collected are described in the “Methods of Data Collection” section of this protocol.

➤ *Sample size and justification:*

A sample size calculation was conducted to determine the number of patients needed to observe a difference in packed red blood cell transfusion rates. In the last two fiscal years at UCHC a hip hemiarthroplasty has been performed in 84 patients, 29 of which required packed red blood cell transfusions (34.5%). We queried the Health Care Utilization Project Database, a stratified 20% national sample of over 7,000,000 hospital stays at over 1,000 hospitals in 46 states, to estimate national rates of packed red blood cell transfusion. In this sample, 14,813 of 45,800 (32.3%) patients undergoing hip hemiarthroplasty in 2011 required a packed red blood cell transfusion. Given these numbers, we used a value for packed red blood cell transfusion rate of 35% for patients that receive placebo. The literature has shown packed red blood cell transfusion rates with use of the drug in an orthopedic setting in similar populations to range from 12.5% to 1%. Accordingly, we selected a packed red blood cell transfusion rate of 10% in patients receiving tranexamic acid. A two group continuity corrected Chi square test with a 0.05 two-sided significance level will have 80% power to detect the difference between packed red blood cell

Topical (*Intra-Articular*) Tranexamic Acid and Transfusion Rates Following Hip ~~Hemiarthroplasty~~

transfusion rates of 35% and 10% (odds ratio of 4.846) when the sample size in each group is 51 (102 total).

➤ *Explain on what basis it is reasonable to assume that the sample size will be obtained:*

The number of hip hemiarthroplasties performed annually has been increasing. In the last fiscal year, 49 hip hemiarthroplasties were performed at UCHC. With a 2-year study period and the possibility that the study may be extended to neighboring facilities (St. Francis Medical Center), it is reasonable to assume the sample size will be obtained.

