transfusion, will be analyzed using a two-group continuity corrected Chi-square test. Differences in packed red blood cell transfusion rates, amount of blood transfused, and inpatient cost will be analyzed using a two-group *t* test. Regression analysis will be used to model packed red blood cell transfusion outcomes against the main predictors (group allocation), adjusting for the effect of covariates (comorbidities, post-operative venous thromboembolism prophylaxis, etc.). Specifically, logistic regression will be used to model packed red blood cell transfusion as a binary outcome (yes or no) and multiple linear regression will be used to model packed red blood cell transfusion amounts and rates. The alpha level for all statistics will be set at 0.05.

5. Timetable

- Expected Start Date: 11/1/15
- General Time Table: 2 years
- Expected Completion Date: 10/31/17

6. Budget / resources:

We have received a Resident Research Project grant award from the Orthopaedic Research and Education Foundation (OREF). The pharmacy, which will play an essential role in this project, has been appropriately budgeted and is available to participate in this study.

7. Dissemination

We plan to disseminate the results of our research in the form of a peer reviewed journal article as well as application for presentation at a national society meetings.

8. References / Literature Review:

Topical (Intra-Articular) Tranexamic Acid and Transfusion Rates Following Hip Hemiarthroplasty

2. Eubanks JD. Antifibrinolytics in Major Orthopaedic Surgery (Review). *J Am Acad Orthop Surg.* 2010;18(3):132-8.

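### If a second hospital opens to reach 102 patients, the single enrollment-order list and the unstratified primary test stay valid but forgo precision that a hospital-stratified test would recover

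*Combined protocol and SAP*

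**What the plan says.** All references are to section 4 (Study Design & Procedures) of the combined protocol and SAP.

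- **Allocation** (study procedures). Before the study starts, "a randomization schedule will be constructed with block randomization using web-based software". Then: "Group assignments will be concealed in opaque sealed envelopes with a numerical code of consecutive numbers reflecting patient enrollment". The envelopes are kept by the pharmacy staff who prepare the drug, and are opened when the patient reaches the operating room. Neither block size nor stratification by hospital is stated.
- **Feasibility** (basis for reaching the sample size). "In the last fiscal year, 49 hip hemiarthroplasties were performed at UCHC". The argument then rests on a two-year period and "the possibility that the study may be extended to neighboring facilities", with one such facility named.
- **Primary analysis** (methods of data analysis). The transfusion rate "will be analyzed using a two-group continuity corrected Chi-square test". A secondary logistic regression adjusts for an open-ended list of covariates in which hospital is not named.
- **Data items** (methods of data collection). Surgeon is listed; hospital is not.

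**The concern.** Whether to transfuse is partly a matter of local practice, so two hospitals may have different underlying transfusion rates. A single list in enrollment order balances the arms overall and over time, but not within each hospital. By chance, one arm can then hold more patients from the hospital that transfuses more. A primary test without a hospital term also leaves the between-hospital variation in its error.

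At stake is some avoidable noise in the primary comparison. There is also a procedural gap: the plan names a possible second hospital but gives no allocation or analysis rule for it, so the rule would have to be made mid-trial.

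**Working it through.** **1. The plan's sample size reproduces.** Inputs from the sample size paragraph: 35% v 10%, two-sided 0.05, 80% power, continuity correction. The mean rate is 0.225.

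- Uncorrected n = [1.96 x sqrt(2 x 0.225 x 0.775) + 0.8416 x sqrt(0.35 x 0.65 + 0.10 x 0.90)]² / 0.25² = (1.157 + 0.474)² / 0.0625 = 42.6, so 43.
- Corrected n = (42.6/4) x [1 + sqrt(1 + 4/(42.6 x 0.25))]² = 10.65 x 4.72 = 50.3, so 51 per arm, as stated.
- Exact power of the corrected test at 51 per arm is 81.6%.

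**2. How likely the second hospital is to be needed.** 2 x 49 = 98, which is below 102 even with every case enrolled. If 80% enroll (assumption), the main hospital gives about 78 and about 24 must come from elsewhere. If 60% enroll, it gives about 59 and about 43 must come from elsewhere.

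**3. Chance imbalance under one list.** Assumptions: 30 of 102 patients from the second hospital, blocks of 4. Ignoring blocks, the number of these 30 in one arm of 51 is hypergeometric, with SD sqrt(30 x 0.25 x 72/101) = 2.31. The between-arm difference therefore has SD 2 x 2.31 = 4.6. A difference of 6 or more (18 v 12 or worse) has probability of about 2 x [1 − Φ(2.5/2.31)] = 28%. Simulation with blocks of 4 also gives about 28%. With separate lists per hospital, simulated at second-hospital shares of 25% and 50%, the arms never differed by as much as 10 points in second-hospital share.

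**4. What an 18 v 12 split does to the estimate.** Relative to 15 v 15, each arm moves by 3 patients in 51. The shift is therefore 3/51 x (gap in placebo rates + gap in drug-arm rates), where drug-arm odds are placebo odds divided by 4.846.

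- Placebo 34.5% and 46.6%: drug arm 9.8% and 15.3%. Shift = 3/51 x (12.1 + 5.5) = 1.0 point.
- Placebo 34.5% and 82.5%: drug arm 9.8% and 49.3%. Shift = 3/51 x (48.0 + 39.5) = 5.1 points.

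For scale, the planned difference is 25 points, with standard error sqrt[(0.35 x 0.65 + 0.10 x 0.90)/51] = 7.9 points.

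**5. Power, with the list and the test separated.** Same assumptions, fixed within-hospital odds ratio, 40,000 simulated trials per setting. MH is the continuity-corrected Mantel-Haenszel test stratified by hospital.

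| Placebo rates | One list, planned test | One list, MH | Separate lists, MH |
|---|---|---|---|
| 34.5% / 46.6% | 84.1% | 84.1% | 85.1% |
| 25% / 60% | 75.7% | 79.3% | 79.8% |
| 34.5% / 82.5% | 77.6% | 85.4% | 85.6% |

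Nearly all of the gain in the second and third rows comes from the test. Separate lists add 0.2 to 1.0 points. Repeat runs put the combined gain at 0.2-1.0, 3.2-4.4 and 7.4-10.0 points in the three rows.

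**6. Sensitivity to how 35% and 10% are read.** Half the patients from each hospital, overall placebo rate 35%.

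| Gap in placebo rates | Pooled 35%/10% held: planned | Pooled: stratified | Odds ratio held within hospital: planned | Odds ratio: stratified |
|---|---|---|---|---|
| 10 points | about 82% | 82.5% | 81.3% | 81.8% |
| 20 points | about 82% | 83.3% | 79.6% | 81.4% |
| 40 points | about 82% | 86.4% | 73.2% | 78.5% |

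**7. Type I error.** With one list and no treatment effect, the planned test rejects in about 3-4% of trials with hospital gaps of the sizes considered. It is not inflated.

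**The case against.** **The second hospital is only a possibility.** It appears in the feasibility paragraph alone, volume is said to be rising, and opening it would need new text on consent and pharmacy anyway. This stands, and it makes the point conditional. But the plan uses that hospital as part of its case for reaching 102, so the allocation and analysis rule can reasonably be written now.

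**The hospital gap is weakly grounded.** The 46.6% and 82.5% come from separate published hemiarthroplasty series, not from neighboring hospitals. The two rates behind the planning value, 34.5% locally and 32.3% nationally, nearly agree. The pair 25%/60% is an assumption with no source in the documents. This stands: the published rates set a range only, and the 82.5% end is extreme.

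**The secondary regression might already include hospital.** The covariate list is open-ended, so it could. The text does not say so, and it would not alter the primary test.

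Three stronger readings are tempting, and the documents do not support them:

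- *The primary result would be biased.* Imbalance under one randomised list is chance only, and the test already allows for it.
- *The trial would be underpowered.* If 35% and 10% are pooled rates, power stays at about 82% at every gap tried. A fall below 80% at the planned 35% overall placebo rate needs a fixed within-hospital odds ratio and a gap of roughly 20 points or more.
- *One envelope series cannot serve two pharmacies.* The plan does not exclude one pharmacy holding the series and relaying assignments. It just does not say how this would work.

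**Conclusion.** The point holds as a minor, conditional improvement. If a second hospital enrolls, the planned list and test remain valid but are less precise than a stratified version with the same number of patients. With 30 of 102 patients from the second hospital, blocks of 4 and a fixed within-hospital odds ratio, a chance imbalance of 6 or more occurs in about 28% of trials and moves the estimate by 1.0 to 5.1 points. The power forgone is 0-1 point when hospitals differ little, 3-4 points at 25%/60%, and about 8 points at the extreme pair.

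The second hospital's share, the block size and the size of the hospital gap are all assumptions; the documents give none of them. The sample size of 51 per arm need not change on this account. If only one hospital enrolls, there is no effect.

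**What to change.** 1. **Methods of data analysis (the main gain).** State that, if more than one hospital enrolls, the primary comparison is the continuity-corrected Mantel-Haenszel test stratified by hospital. With a single hospital of 102 patients this statistic equals the planned one multiplied by 101/102, so nothing material changes.
2. **Methods of data collection.** Add hospital as a data item.
3. **Study procedures.** State that each hospital has its own permuted-block schedule and its own numbered envelope series, created before that hospital enrolls. This adds at most about one point of power but keeps hospital balanced between the arms.

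Item 3 should not be adopted without item 1. Separate lists analysed with the unstratified test make that test more conservative: with a 40-point gap and equal shares, its type I error falls from 3.1% under one list to 1.8%.

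The cost is one more schedule from the same software, one data field and a few sentences. The downside is at most one incomplete block per hospital. No extra patients are needed.

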If an LAR is required to provide informed consent, obtaining informed consent from the LAR and assent from the patient will occur in the patient's room with both the patient and LAR present so that communication regarding the study is not withheld from the patient despite his or her decisional impairment. If the LAR is not in the hospital, the LAR will be contacted in the manner that the orthopaedic surgery service contacted the LAR (e.g. by phone). If the LAR indicates that he or she is planning on coming to the hospital prior to the surgical intervention, informed consent for study inclusion will be sought at this time so that a face-to-face consent process can occur. If the LAR does not plan to come to the hospital before the surgical intervention or the LAR is unable to come to the hospital, the patient will not be eligible for study inclusion.

Once informed consent is obtained, the pharmacy will be contacted to allow provision of the study drug at the time of the procedure. When the patient is brought to the operating room, the pharmacy staff will open the numerical envelope assigned for the specific patient. The patient will undergo a hip hemiarthroplasty, according to the standard of care for a displaced femoral neck fracture. Surgical approach and implant selection will be left to the discretion of the attending surgeon. The only difference associated with study participation is that prior to wound closure, either a resident performing the surgery or the attending physician will introduce 1 gram

Topical (*Intra-Articular*) Tranexamic Acid and Transfusion Rates Following Hip Hemiarthroplasty

of tranexamic acid (APP Pharmaceuticals LLC, Schaumburg, IL) mixed with normal saline (0.9% NaCl) for a total volume of 50 cc or a 50 cc normal saline placebo into the wound. Of the 50 cc of the study drug or placebo, 25 cc will be introduced intra-articularly and 25 cc will be introduced under the fascial layer. When introducing either the study drug or placebo, the resident or attending physician should attempt to coat all surfaces with a thin layer of the aqueous solution. Wound closure technique will be left to the discretion of the attending surgeon. Post-operative venous thromboembolic prophylaxis will be left to the discretion of the attending surgeon.

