Because patients sustaining femoral neck fractures rarely undergo surgical intervention in the same day, they are typically given a dose of either enoxaparin or heparin upon admission to prevent deep vein thrombosis given their injury and immobility. Patients receive this medication each day until the day of their surgical intervention, at which time this medication is held to prevent excessive intra-operative blood loss. The drug is resumed on post-operative day 1 for deep vein thrombosis prophylaxis. The drug insert for enoxaparin states, “significant anti-factor Xa activity persists for 12 hours following a 40 mg subcutaneous once a day dosing.” Because this medication is held on the day of surgery, there is greater than 12 hours from the last dose received until the surgical intervention. Patients who receive either enoxaparin or heparin will be included in the study. We will record the use of these medications (e.g. enoxaparin and heparin) and the interval between the last dose of medication and the surgical intervention for covariate analysis. Given how common the in-hospital use of these medications is in patients prior to undergoing hip hemiarthroplasty, we expect to achieve balanced groups through the process of randomization. Coagulation labs (PT/PTT/INR), when obtained prior to surgery, will be recorded to demonstrate similarity between the groups.

➤ *Describe length of subject’s participation in the study including number of visits, frequency of visits, and length of visits:*

Patients will be in the study for 4 to 6 weeks. This time period will encompass their inpatient hospital stay and their first two outpatient visits (one at approximately 2 weeks, a second at 4-6 weeks). These visits are the regularly scheduled post-operative visits that are part of routine care follow up. No extra time per visit or number of visits will be required as a result of study inclusion. The scheduled date of the patient’s post-operative outpatient visit occurring between 4 and 6 weeks will reflect the last day of study involvement.

➤ *Methods of Data Collection and Types of Data to be collected:*

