All data will be collected using an IRB approved data collection form. Data will consist of demographic information (age, gender, body mass index, injury side, comorbidities, etc.), pre- and postoperative blood values (hematocrit/hemoglobin, PT/PTT/INR (if obtained), etc.), pre-operative anti-platelet use (aspirin, etc.), pre-operative heparin or enoxaparin use and interval between last dose and the surgical procedure, time from admission to surgical intervention, intra-

operative details (approach, cemented vs. un-cemented, surgeon, operative time, anesthesia, and estimated blood loss), packed red blood cell transfusion rates and amount, length of inpatient stay, prescribed chemoprophylaxis, complications (transfusion related complications, deep vein thrombosis, pulmonary embolism, myocardial infarction, stroke, death, infection, hematoma), and inpatient cost. Detailed list of the data to be collected as well as time points of collection can be found in the attachment to this labeled “Data Collection Forms.”

The primary outcome measure is the rate of packed red blood cell transfusion. Secondary outcome measures include amount of packed red blood cell transfusion, difference between pre- and postoperative hemoglobin/hematocrit, length of stay, complications, and inpatient cost.

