APPENDIX A

Additional Details Pertaining to Study Design for Clinical Trials

Appendix A must be completed for investigator/student initiated research projects that require review by the convened board. For example, studies that use investigational test articles, that present more than minimal risk to subjects, or that involve prisoners, must be reviewed by the convened board.

Topical (*Intra-Articular*) Tranexamic Acid and Transfusion Rates Following Hip ~~Hip Arthroplasty~~

Note that for studies requiring review by the convened board the full board application must be completed, data safety monitoring must be addressed (e.g. by completion of Appendix B to the main application) and the Investigator Brochure and /or package insert must also be submitted if available.

1. *For a clinical trial (e.g. a Phase I, II or III study), the use of the intervention must be fully described e.g., the treatment regimen for use of drugs, placebo, medical device etc. Also include plans for receipt of test article, storage, dispensing and reconciliation.* : The intervention, the application of either 1 gram of tranexamic acid mixed with normal saline (0.9% NaCl) for a total volume of 50 cc or 50 cc of normal saline (0.9% NaCl) placebo, will occur intra-operatively just prior to wound closure. One half, or 25 cc, of either the study drug or the saline placebo will be applied intra-articularly. The second half, or 25 cc, will be applied under the fascia. When applying either the study drug or saline placebo, the resident performing the case or the attending surgeon will attempt to coat all exposed tissues with a thin layer of the aqueous solution. This is a one-time dose. Provision of the study drug (Tranexamic acid or saline placebo) will be provided by the hospital pharmacy. The pharmacy is responsible for the storing and dispensing the study drug.

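### The primary transfusion outcome has no stated start or end, so read literally it includes transfusions given before the solution is applied, which can only attenuate the treatment difference

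*Combined protocol and SAP*

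**What the plan says.** All references are to the combined protocol and SAP.

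- **Outcome.** The data collection part of section 4 states that "The primary outcome measure is the rate of packed red blood cell transfusion". The data analysis part compares it with a continuity-corrected chi-square test and adds that "logistic regression will be used to model packed red blood cell transfusion as a binary outcome (yes or no"). Neither part says from when, or until when, a transfusion counts.
- **Intervention.** Section 4 says that "prior to wound closure, either a resident performing the surgery or the attending physician will introduce 1 gram" of tranexamic acid in saline, or saline alone. Appendix A, item 1, confirms that application "will occur intra-operatively just prior to wound closure" and is a single dose.
- **Allocation.** "When the patient is brought to the operating room, the pharmacy staff will open the numerical envelope assigned for the specific patient".
- **Wait before surgery.** The exclusion criteria text notes that "patients sustaining femoral neck fractures rarely undergo surgical intervention in the same day". On length of participation, section 4 says: "This time period will encompass their inpatient hospital stay and their first two outpatient visits".
- **Planning rates.** The 35% placebo rate rests on 84 local patients, "29 of which required packed red blood cell transfusions (34.5"%), and on a national sample with 32.3%. The 10% drug rate is taken from published rates with the drug of 12.5% to 1%. No timing restriction is stated for any of these.
- **Time points.** Collection time points are referred to an attached set of data collection forms, which is not among the documents reviewed.

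**The concern.** A patient can be given red cells on the ward before surgery, or in theatre before closure. The solution has not yet been applied, so it cannot prevent that unit. A ward transfusion even precedes the opening of the envelope. If such a patient counts as an event, the event is equally likely in both arms and tells nothing about the drug. It adds a common amount to both rates, moves the relative risk towards 1 and costs power.

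The sample size has little room for this: 51 per arm is the smallest number that meets 80% power on the planned rates, and no allowance for loss is stated. There is also a practical risk. Without a written window, someone has to decide during or after the trial which transfusions count, and in 102 patients a few reclassified cases could change the result.

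**Working it through.** **Inputs.** From the sample size section: placebo 35%, drug 10%, two-sided 0.05, 80% power, continuity-corrected chi-square, 51 per arm. The planned relative risk is 0.10/0.35 = 0.286. The one input the documents lack is q, the share of all patients transfused before application. It is assumed here at 2, 5 and 10 percentage points.

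**The plan's own figure.** With p̄ = 0.225 and d = 0.25, the uncorrected size is

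n = [1.960 × √(2 × 0.225 × 0.775) + 0.842 × √(0.35 × 0.65 + 0.10 × 0.90)]² / 0.25² = 42.6.

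The continuity correction gives (42.6/4) × [1 + √(1 + 4/(42.6 × 0.25))]² = 50.3, rounded up to 51. The stated size is reproduced. Exact enumeration of the corrected test at 51 per arm gives power of 81.6%. All power figures below use the same enumeration.

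**Reading 1: 35% is a whole-stay rate, and the planned ratio acts only on post-application transfusions.**

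- As written: placebo 0.35; drug q + (0.35 − q) × 0.286. For q = 0.05 this is 0.05 + 0.30 × 0.286 = 0.136.
- Post-application only: placebo 0.35 − q; drug (0.35 − q) × 0.286. A patient transfused only before application is a non-event and stays in the denominator.

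| q | As written | Power | Post-application only | Power |
|---|---|---|---|---|
| 0 | 35% v 10.0% | 81.6% | 35% v 10.0% | 81.6% |
| 2% | 35% v 11.4% | 74.9% | 33% v 9.4% | 78.0% |
| 5% | 35% v 13.6% | 63.8% | 30% v 8.6% | 72.1% |
| 10% | 35% v 17.1% | 44.6% | 25% v 7.1% | 60.4% |

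The narrower window gains about 3, 8 and 16 points. It does not bring power back to 80% at 51 per arm, because the placebo rate on that window is itself lower. By the sample size formula above, 80% power needs 58, 71 or 105 per arm as written and 55, 61 or 76 on the narrower window.

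**Reading 2: 35% and 10% are both whole-stay rates.** The 10% then already contains any pre-application transfusions, and the outcome as written keeps its 81.6%. Taking q from both arms gives 33% v 8% with power 84.7% at q = 2%, and 30% v 5% with power 90.3% at q = 5%. At q = 10% no drug-arm transfusion would remain after application, so that value is not informative here.

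**Reading 3: 35% and 10% are both post-application rates, with q added independently.** As written, the rates are q + (1 − q) × 0.35 and q + (1 − q) × 0.10. Power is 77.5%, 71.6% and 62.1% for q = 2%, 5% and 10%. Counting only post-application transfusions gives back 81.6%.

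For every non-zero q shown under each reading, the post-application window has more power than the literal whole-stay outcome.

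**The case against.** The strongest reply is that the key input is missing. Nothing in the documents says that any patient is transfused before application; they show only that there is time for it. If the share is small, so is the effect: on reading 1, power is 78% as written against 80% at 1 point, and 80% against 81% at half a point. This stands, and it is why the size can be given only as a range.

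Other points deserve weight:

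- **The study title speaks of transfusion rates *following* hemiarthroplasty.** That suggests a postoperative intent, so it goes too far to say the sponsor chose to count earlier transfusions. But a title is not an outcome definition. The one dated start, the day of surgery in the mortality stopping rule (Appendix A, item 4), is not tied to transfusion and would still admit units given in theatre before closure.
- **The data collection forms may already record timing.** They may. Recording a time does not settle which transfusions count.
- **A whole-admission rate is a defensible pragmatic outcome**, since the aims include cost per admission. This is a reason to keep reporting it. The hypothesis, however, concerns the effect of the solution.
- **Randomization balances earlier transfusions on average.** It does, so a reader who infers bias towards either arm would be wrong. Balance does not prevent attenuation.

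A reader might also infer that the move from 35% to 10% treats every transfusion as preventable. The plan does not say so: it leaves 10% of treated patients transfused, and that figure may already include transfusions that the drug could not have prevented.

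**Conclusion.** The point holds as a gap in the outcome definition with a possible cost in power. The protocol gives the primary outcome no window, and a literal reading admits events that precede treatment. The consequence is attenuation only, and it is nil if no one is transfused before application.

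The loss depends on two things the documents do not settle: the pre-application share, and what the 35% and 10% rates cover. On reading 1, power as written falls from about 82% to 75%, 64% or 45% for shares of 2, 5 or 10 points. On reading 2 it does not fall at all. The documents therefore do not show that the trial is underpowered, and the stated sample size is correct for its inputs. The case for the change does not depend on choosing a reading: with any non-zero share examined, the post-application window does better under all three, and with a zero share it loses nothing.

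**What to change.** 1. Define the primary outcome as at least one unit of packed red cells started after application of the study solution and before discharge. If the solution was not applied, count from the start of wound closure. Appendix A, item 3, foresees such patients, and this gives them a defined window too.
2. Use the same window for the amount transfused.
3. Record transfusion before that point as a yes/no baseline covariate in the logistic model. It precedes treatment and is decided by blinded staff, so it is a legitimate adjustment variable.
4. Report any transfusion during the admission as a sensitivity analysis.
5. Confirm that the data collection form captures the start time of each transfusion, and add it if it does not.
6. Check the 35% planning rate on the same window, for example by looking up transfusion timing in the 29 transfused patients among the 84 local cases, and restate the power. On reading 1 the new definition alone does not restore 80% at 51 per arm.

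The cost is a short definition, possibly one field on a form, and a small chart review. The one downside is that the main result is no longer the whole-admission rate, which is still reported.
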